6.2.2 Stopping Rules for Multiple Subjects

If 2 subjects experience a similar severe event or SAE, or any subject experiences a life threatening AE that is considered to be at least possibly related to SBC-103, dosing will be stopped for this study. The independent Safety Review Committee and the Sponsor will evaluate the data and will resume dosing only after review and agreement, including review and approval by local regulatory authorities, where required.

Detailed information regarding the composition of the SRC, the safety data to be reviewed, and the data review process will be included in the SRC charter.

Either of the SRC and Sponsor may request a pause in dosing of all subjects based on review of reported events and all available data from this and other studies in the program. Dosing will resume only after the review of data and agreement to do so by the SRC and Sponsor.

6.3 Description of SBC-103

The reference document for SBC-103 is the Investigator Brochure. SBC-103 must be administered under close supervision of the Investigator, or designee.

The study drug will be provided in a 10-mL glass vial containing approximately 10.5 mL (including 5% overfill) of a buffered solution of SBC-103 at a concentration of 2 mg/milk The study drug contains no preservatives and vials are single use only.

6.4 Method for Assigning Subjects to Treatment Groups

Not applicable as there is only 1 treatment group in this study.

6.5 Storage and Disposition of SBC-103

6.5.1 Receipt of Drug Supplies

Upon receipt of the study treatment supplies, an inventory must be performed and a drug receipt log filled out and signed by the person accepting the shipment. It is important that the designated study staff counts and verifies that the shipment contains all the items noted in the shipment inventory. Any damaged or unusable SBC-103 in a given shipment will be documented in the study files. The Investigator must notify study Sponsor of any damaged or unusable study treatments that were supplied to the Investigator's site.

6.5.2 Storage

All SBC-103 vials must be stored at a controlled temperature of 2°C to 8°C. Vials should not be frozen and should be protected from light during storage.

The infusion bag or syringe containing SBC-103 diluted in 0.9% saline should be prepared immediately before infusion. Dilution should occur under controlled and validated aseptic conditions. The prepared diluted infusion bag (or syringe) may be stored at room temperature (20°C to 25°C) for no more than 8 hours, although it is preferable that prepared solution be used within 4 hours of dilution. Shaking or other forms of agitation of vials or infusion bags should be avoided. Refer to the IMP Manual for detailed instructions.

6.5.3 Disposition

The Investigator or designee (e.g., a licensed pharmacist) will be responsible for maintaining accurate records for all supplies used. Opened vials of SBC-103 containing residual volume will be stored at room temperature for SBC-103 accountability. Following SBC-103 accountability, the Sponsor will provide authorisation to the Investigator to return or destroy any remaining investigational product as instructed.

Under no circumstances will SBC-103 be used other than as directed in the protocol. Refer to the IMP Manual for additional details.

6.6 Preparation and administration of Study Drug

6.6.1 Preparation of Study Drug

Dose preparation and administration should be performed using sterile, non-pyrogenic disposable materials including, but not restricted to syringes, needles, transfer tubing, and stopcocks.

The infusion bag (or syringe) containing SBC-103 should be prepared just prior to the start of IV infusion. It is preferable that the prepared diluted infusion is used within 4 hours of dilution, although it may be stored at room temperature for up to 8 hours.

Prior to preparation of the infusion, the vials of study drug should be visually inspected. The solution should not be used if it contains foreign particulate matter or is discoloured. The solution may be used if a small number of visible translucent to opalescent or white amorphous or threadlike particles are present in the vial. The contents should NOT be warmed using a microwave or other heat source. SBC-103 is a protein and should be not be shaken but should be handled and mixed gently to prevent foaming.

The subject's most recent protocol-scheduled weight measurement, rounded to the nearest 0.1 kg, will be used for calculating the volume of study drug to be withdrawn from the vial(s) to prepare the IV infusion. Study drug will be diluted in 0.9% saline for injection.

Refer to the IMP Manual for detailed instruction regarding the preparation of the IV infusion.

6.6.2 Administration of Study Drug

All infusions must be administered under close supervision of the Investigator, or designee. Study drug should not be infused with other products in the same infusion tubing, as the compatibility of SBC-103 in solution with other products has not been evaluated. It is recommended that all infusions of study drug be administered using in-line filtration with a low protein binding 0.2 μ m filter.

The recommended duration of the infusion is 2 hours at a constant rate. The protocol allows for a change in rate should the subject experience an IAR. At the discretion of the Investigator, and in consultation with the Sponsor, in circumstances such as a prior IAR or other like situations where subject safety is a concern, an extended duration of infusion or a variable rate is acceptable. If the infusion is not well tolerated, the infusion rate may be decreased or interrupted as noted in Section 7.1.3 and Section 6.2. All changes to infusion rate must be carefully recorded in the CRF, including the start and stop time of each rate change.

Refer to the IMP Manual for detailed instruction on the administration of SBC-103.

6.7 Blinding of SBC-103

This is an open label study with no requirement for blinding.

6.8 Destruction of SBC-103

If any unused study drug material is remaining upon completion of the study, the material will be returned to the Sponsor or designee or destroyed only after the Sponsor or designee has performed final drug accountability and provided written authorization for the return or destruction of study drug. Refer to the IMP Manual for further instructions.

7 ASSESSMENT OF SAFETY

The methods for collecting safety data are described below. All personnel involved with the study must ensure they are familiar with the content of this section.

7.1 Adverse Events and Laboratory Abnormalities

7.1.1 Clinical Adverse Events

An AE is any untoward medical occurrence in a subject, which does not necessarily have to have a causal relationship with the administration of a study drug. An AE can therefore be any unfavourable and unintended sign, symptom or disease temporally associated with the use of the study drug, whether or not considered related to the medicinal product. Pre-existing conditions that worsen in severity during the course of the study are to be reported as AEs.

All AEs occurring during the clinical study will be reported in the AE page of the CRF.

The Investigator will assess the severity, causality (relationship to study drug), and seriousness of each AE.

Severity: The Investigator will assess the severity of all AEs/SAEs as mild, moderate, or severe, based on the following definitions, developed from Clinical Data Interchange Standards Consortium Study Data Tabulation Model standard terminology v3.1.1).

- **Mild:** A type of AE that is usually transient and may require only minimal treatment or therapeutic intervention. The event does not generally interfere with usual activities of daily living.
- **Moderate:** A type of AE that is usually alleviated with additional specific therapeutic intervention. The event interferes with usual activities of daily living, causing discomfort, but poses no significant or permanent risk of harm to the research participant.
- Severe: A type of AE that interrupts usual activities of daily living, or significantly affects clinical status, or may require intensive therapeutic intervention.

Causality: AEs will be assessed as not related, unlikely related, possibly related, or related to study drug. Table 3 provides general guidance on the assessment of causality. For data reporting purposes, AEs assessed as not related or unlikely related will be classified as unrelated to study drug, and AEs assessed as possibly related or related will be classified as related to study drug. Assessment of causality should be based on the Investigator's medical judgment and the observed symptoms associated with the event.

Relationship to Study Drug	Criteria for Judgment
Related	Reasonable temporal relationship of the clinical event to study drug administration AND cannot be reasonably explained by other factors (such as the subject's clinical state, concomitant therapy, and/or other interventions).
Possibly Related	The temporal relationship of the clinical event to study drug administration makes causal relationship possible but not unlikely AND other drugs, therapeutic interventions, or underlying conditions do not provide a sufficient explanation for the observed event.
Unlikely Related	The temporal relationship of the clinical event to study drug administration makes causal relationship unlikely but not impossible AND other drugs, therapeutic interventions, or underlying conditions provide a plausible explanation for the observed event.
Not Related	Data are available to clearly identify an alternative cause for the reaction.

Table 3:	Assessment of Causality
1 4010 01	rissessment of Causanty

Seriousness: AEs will be classified as serious or non-serious according to the definitions provided below.

An SAE is any AE that is or leads to any of the following:

- Death.
- Immediately life threatening. An AE is considered "life threatening" if, in the view of either the Investigator or Sponsor, its occurrence places the subject at immediate risk of death. It does not include an AE that, had it occurred in a more severe form, might have caused death.
- Requires in-patient hospitalisation or prolongation of existing hospitalization.
- Congenital anomaly/birth defect.
- Persistent or significant disability or incapacity.
- An important medical event that may not result in death, be life threatening, or require hospitalization may be considered an SAE when, based upon appropriate medical judgment, the event may jeopardise the subject and may require medical or surgical intervention to prevent one of the outcomes listed above.

A planned hospitalization to accommodate a study procedure is not considered an SAE. However, during the hospitalization, AEs will be collected and assessed for seriousness and reported appropriately (i.e., important medical event or prolonged hospitalization). All AEs that do not meet any of the criteria for an SAE should be regarded as *non-serious AEs*.

All SAEs and IARs must be reported to the Sponsor as described in Section 7.4.1.

7.1.2 Laboratory Test Abnormality

Laboratory test results will be recorded, or appear on the laboratory reports submitted directly from the laboratory. Out-of-range laboratory test values should not be reported as AEs unless they are considered to be clinically significant abnormalities by the Investigator.

7.1.3 Adverse Events of Special Interest (Infusion-Associated Reactions)

IARs will be considered AEs of special interest. Any AE that occurs during the infusion or within 4 hours after the infusion is completed and is assessed by the Investigator as at least possibly related to study drug will be designated as an IAR. In addition, if, at any time during the study, the Investigator observes symptoms that he/she considers to be consistent with an IAR or hypersensitivity reaction related to administration of study drug, the symptoms should be recorded as an AE(s) and designated as an IAR(s). Individual AE terms should be recorded rather than the terms IAR or Infusion Associated Reaction.

As with any ERT, medications and equipment for the treatment of hypersensitivity reactions must be available for immediate use in case of unexpected, severe hypersensitivity reaction. These supplies include, but are not limited to, oxygen, antipyretics, antihistamines (e.g., diphenhydramine: parenteral and oral), corticosteroids, epinephrine, beta-adrenergic inhalers, and cardiopulmonary resuscitation devices.

General guidelines for classifying the severity of a reaction are provided in Section 7.1.1.

For similar biological products, most acute IARs occur within 2 hours of the infusion. Signs of a possible acute IAR may include:

• Hyperemia, flushing, fever and/or chills, nausea, pruritus, urticaria, gastro-intestinal symptoms (vomiting, diarrhoea, abdominal cramping), cardiopulmonary reactions, including chest pain, cardiac arrhythmias, dyspnoea, wheezing, stridor, hypotension, or hypertension.

Table 4 includes dose modifications required for all IARs and general guidance for the diagnosis and management of IARs in accordance with the institution's standard of care. The Investigator should use clinical judgement in the management of IARs in individual subjects participating in this study. In the case of a severe life-threatening reaction, current medical standards for emergency treatment are to be followed.

Symptoms	Action		
Mild Reaction Common • Hyperemia (flushing) • Flushing • Lightheadedness • Nausea • Mild chest discomfort (tightness) Less Common • Fever and/or shivering • Palpitations • Irritability (especially in young children)	 Slow infusion rate by 50% Administer antipyretic and/or antihistamine Decrease infusion rate by a further 25% if symptoms persist If the event resolves, the infusion should continue at a reduced rate for a minimum of 30 minutes before the infusion is increased to 75% of original rate. If the subject tolerates the infusion at 75% of the original rate for at least 30 minutes the original rate may be restored for the remainder of the infusion. If reactions persist despite rate reduction, stop infusion Pre-treat with antihistamine and antipyretic prior (approximately 1.5 hours) to next infusion e.g., diphenhydramine (1 mg/kg) by mouth and acetaminophen (15 mg/kg) by mouth 		
 Moderate Reaction Hyperemia (flushing) Chest discomfort Itching and/or raised urticarial rash Severe headache Gastrointestinal symptoms, vomiting, diarrhoea, abdominal cramping 	 Stop infusion Give antihistamine IV and consider IV or oral steroids in accordance with institutional standard of care Consider giving a beta-adrenergic inhaler treatment if appropriate If the event resolves, the infusion may continue at a reduced rate of 50% of the original for a minimum of 30 minutes before the infusion is increased to 75% of the original rate. If the subject tolerates the infusion at 75% of the original rate for at least 30 minutes the original rate may be restored for the remainder of the infusion. If reaction persists despite rate reduction stop infusion Pre-treat with oral antihistamine and antipyretic prior to next infusion Collect serum for analysis of tryptase 1-3 hours after the IAR onset and another serum sample for tryptase and ADA during the next study visit (≥ 4 days after the IAR) prior to the infusion. 		

Table 4:Guidelines for the Management of Infusion-associated Reactions
(IARs)

Г

7.2 Handling of Safety Parameters

7.2.1 Serious Adverse Events and Infusion-Associated Reactions (Immediately reportable to the Sponsor)

All SAEs and all IARs (serious and non-serious), irrespective of the treatment received by the subject, must be reported to the Sponsor or designee immediately and no later than 24 hours of the Investigator's first knowledge of the event (expedited reporting).

The definition and reporting requirement are in accordance with ICH Guideline for Clinical Safety Data Management, Definitions and Standards for Expedited Reporting (Topic E2, 1995).

7.2.2 Adverse Event Reporting Period

The study period during which AEs must be reported is defined as the period from signature of the informed consent to the end of the study treatment follow-up. AEs occurring after signing the informed consent but prior to the first dose of study medication will only be recorded if assessed as related to protocol procedures or requirements. For this study, the study treatment follow-up is defined as a minimum of 30 days following the last administration of study treatment. If a subject experiences an SAE that is considered to be related to study treatment at any time after the study, it must be reported to the Sponsor.

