5.2.5 Telephone Calls

A follow-up telephone call will be made to each subject (or the subject's parent or caregiver) within 24 hours after each of the subject's second, third, and fourth doses to assess AEs.

At least 4 weeks after a subject's last dose of SBC-103 is administered, the subject (or the subject's parent or caregiver) will receive a follow-up phone call to assess AEs and concomitant medications unless the subject has a scheduled follow-up study visit.

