7.3 Recording of Adverse Events

At each contact with the subject (and the subject's parent or caregiver), the Investigator must seek information on AEs by specific questioning and, as appropriate, by examination. Information on all AEs should be recorded immediately in the source documentation and in the CRF. All clearly related signs, symptoms, and abnormal diagnostic procedures results should be recorded under a single diagnosis.

AEs will be recorded from the time of signing of the informed consent until completion of the last scheduled visit, i.e., the follow-up visit. AEs occurring after signing the informed consent but prior to the first dose of study medication will only be recorded if assessed as related to protocol procedures or requirements. Any AEs remaining unresolved should be recorded as ongoing. Ongoing AEs/SAEs should continue to be followed up for the period specified in Section 7.2.2 but without further recording in the CRF. However, follow-up information on SAEs must be reported to the Sponsor or designee as described in Section 7.4.1. Any SAE that occurs after the study period and is considered to be possibly related to the study treatment or study participation should be recorded and reported immediately.

Any AE that occurs within 24 hours of the infusion will be recorded by time and date. AEs occurring more than 24 hours after the infusion will be recorded by date only. The date and time, or the date when the AE started and stopped, as well as the intensity, seriousness, action taken with regard to the SBC-103, causality assessment and outcome of the event will be recorded for each AE.

7.4 Reporting of Serious Adverse Events, Infusion-Associated Reactions, and Unanticipated Problems

Investigators and the Sponsor must conform to the AE reporting timelines, formats, and requirements of the various entities to which they are responsible (§13 GCP-V; Detailed guidance on the collection, verification and presentation of AE/reaction reports arising from clinical trials on medicinal products for human use ['CT-3']; US CFR Title 21, §312.32, Investigational New Drug [IND] safety reporting). The Sponsor or designee will report all reportable events to all Regulatory Authorities, IECs or IRBs, and Investigators as required by local regulations.

All SAEs and IARs, and other reportable events (see Section 7.4.3) must be reported to the Sponsor or designee in an expedited manner according to timelines described in Section 7.4.1.

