Calbindin D, HGF, Tau, pTau, Amyloid β, Albumin, IgG in CSF								X ^p					X ^p	
Glutamic Acids and Glycine in CSF								X^{P}					X^P	
Routine Findings (Cell Counts, Glucose, Protein) in CSF ³								X ^P					X ^P	
SBC-103 in CSF								X ^P					X ^P	
SBC-103 Dosing	Х	Х	Х	Х	Х	Х	Х	Х	Х	Х	Х	Х	Х	Х
Adverse Events ¹⁰							CONTI	NUOUS						
Concomitant Medications ¹¹							CONTI	NUOUS						

Page 99 of 104

Assessments	Week 134	Week 136	Week 138	Week 140	Week 142	Week 144	Week 146	Week 148	Week 150	Week 152	Week 154	Week 156/ End of Treatment/ Early Termination	Week 160
	±5	± 5	±5	±5	± 5	± 5	± 5	± 5	± 5	±5	±5	±5	± 5
Visit Window (Days)	days	days	days	days	days	days	days	days	days	days	days	days	days
Physical Examination		X ^P		X ^P		X ^P		X ^P		X ^P		X ^P	
Height and Weight		X ^P		X ^P		X ^P		X ^P		X ^P		X ^P	
Vital Signs ¹²	Х	Х	Х	Х	Х	Х	Х	Х	Х	Х	Х	Х	
12-lead ECG ¹												X ^P	
FDNA												Х	
Vineland-II, BSID-III, KABC-II, BOT-2 Brief Form, CSHQ, CCC-2, SBRS, ZBI, SF-10 ²												X ^p	
Haematology, Serum Chemistry (including Coagulation), Urinalysis ³			X ^p				X ^p					X ^p	
Serum Albumin sample					Х								
Pregnancy Test (Urine) ⁴		X ^P		X ^P		X^P		X ^P		X ^P		X ^P	
Serum and Urine Heparan Sulphate (Total and NRE)			X^{P}		X^{P}		X^{P}					X^{p}	
Serum Ferritin and Chitotriosidase			X^{P}				X^{P}					X^{p}	
Plasma Glutamic Acid and Glycine			X^{P}				X^{P}					X^{P}	
Serum Biomarkers (Exploratory including IgG, inflammatory markers)			X ^P				X ^P					X ^p	
Serum Pharmacokinetic Profile ⁵												Х	

Page 100 of 104

Assessments	Week 134	Week 136	Week 138	Week 140	Week 142	Week 144	Week 146	Week 148	Week 150	Week 152	Week 154	Week 156/ End of Treatment/ Early Termination	Week 160
Visit Window (Days)	±5 days	±5 days	±5 days	±5 days	±5 days	±5 days	±5 days	±5 days	±5 days	±5 days	±5 days	±5 days	±5 days
SBC-103 ADA ⁶	uays	X ^P	uays	X ^P	uays	X ^P	uays	X ^P	uays	X ^P	uays	XP	uays
General Anaesthesia/Sedation ⁷					X ^P							X ^p	
Lumbar Puncture ^{7,8}					X ^P							X ^p	
Heparan Sulphate (Total and NRE) in CSF					X ^P							X ^p	
Calbindin D, HGF, Tau, pTau, Amyloid β, Albumin, IgG in CSF					X ^p							X ^p	
Glutamic Acids and Glycine in CSF					X ^P							X ^p	
Routine Findings (Cell Counts, Glucose, Protein) in CSF ³					X ^p							X ^p	
SBC-103 in CSF					X ^P							X ^P	
Structural and Diffusion MRI ⁷												X ^P	
Telephone call ⁹													Х
SBC-103 Dosing	Х	Х	Х	Х	Х	Х	Х	Х	Х	Х	Х	Х	
Adverse Events ¹⁰		CONTINUOUS											

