Concomitant Medications ¹¹		CONTINUOUS											

Assessments	Week 134	Week 136	Week 138	Week 140	Week 142	Week 144	Week 146	Week 148	Week 150	Week 152	Week 154	Week 156/ End of Treatment/ Early Termination	Week 160
	±5	±5	±5	±5	±5	±5	±5	±5	±5	±5	±5	± 5	±5
Visit Window (Days)	days	days											

Key: ADA = anti-drug antibodies; BOT-2 Brief Form = Bruininks-Oseretsky Test of Motor Proficiency, Second Edition, Brief Form; BSID-III = Bayley Scales of Infant and Toddler Development, Third Edition; CCC-2 = Children's Communication Checklist, Second Edition; CSF = cerebrospinal fluid; CSHQ = Children's Sleep Habits Questionnaire; D = day; ECG = electrocardiogram; FDNA = Facial Dysmorphology Novel Analysis; HGF = hepatocyte growth factor; IgG = immunoglobulin G; KABC-II = Kaufman Assessment Battery for Children, Second Edition; NAGLU = alpha-N-acetylglucosaminidase; MRI = magnetic resonance imaging; NRE = nonreducing end; SBRS = Sanfilippo Behavior Rating Scale; SF-10 = Short Form Health Survey for Children; Vineland-II = Vineland Adaptive Behavior Scales, Second Edition; Wk = week; ZBI = Zarit Burden Interview, 12-item.

*All study visits will be scheduled relative to Day 0. Infusions will be administered every 14 days \pm 5 days and must be administered at least 10 days apart. Informed consent may be granted before the beginning of the screening period. All screening assessments other than informed consent should be completed within a 28-day window.

X^P Assessments to be performed pre-dose

¹ ECG assessments after 6 months do not need to be performed in triplicate.

² The Vineland-II, BSID-III or KABC-II, BOT-2 Brief Form, and CCC-2 should be administered in-person by an appropriately qualified professional.

- ³ Local lab ranges will be used for those labs analysed locally. If samples are taken within 3 days of Day 0, samples do not need to be repeated on Day 0. However, a Day 0 serum sample for albumin should be collected at the same time as the CSF collection, to enable calculation of CSF-AI. Central laboratory parameter reference ranges will be used throughout the study, including in the event that laboratory parameters are analysed locally. All attempts should be made to draw laboratory samples for central laboratory analysis when samples are needed for local analysis. Day 1 samples will be analysed locally, all other samples may be analysed centrally.

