- ⁴ If a urine sample is not able to be provided, a serum pregnancy test will be performed by a local laboratory.
- ⁵ Refer to Section 5.2.1.2 for directions and timing of PK sampling.
- ⁶ In addition to time points indicated, obtain a sample for ADA determination anytime subject experiences a moderate-to-severe IAR during the next study visit (≥ 4 days after the IAR) and prior to the infusion.
- ⁷ Lumbar puncture and MRI procedures may be performed under general anaesthesia or light sedation, as clinically appropriate in accordance with local institutional procedures. If clinically indicated, subjects may also receive general anaesthesia or sedation for central line placement for long-term vascular access, in accordance with institutional guidelines. When possible, the procedure to place the central line should be performed while the subject is already anaesthetised or sedated for another study procedure. After the lumbar puncture is completed, the subject should be observed as per institution standard practice. Vital signs, adverse events, and concomitant medications should be assessed before the subject is discharged from the site.
- ⁸ During study visits where CSF is collected, and no serum chemistry sample is indicated per the SOA, a serum albumin sample should be collected to assess CSF-AI. After the lumbar puncture is completed, the subject should be observed as per institution standard practice.

Page 102 of 104

Assessments	Week 134	Week 136	Week 138	Week 140	Week 142	Week 144	Week 146	Week 148	Week 150	Week 152	Week 154	Week 156/ End of Treatment/ Early Termination	Week 160
Visit Window (Days)	±5	±5	±5	±5	±5	±5	±5	±5	±5	±5	±5	±5	±5
	days	days											

A telephone follow-up call will be made 4 weeks after the last dose received of SBC-103 after Week 156 End of Treatment or after the Early Termination visit.

¹⁰ All AEs should be followed until they have returned to baseline values or stabilised or until the Investigator and Sponsor or designee agree that follow-up is no longer necessary.

¹¹ Information on all medications and treatments received by the subject within the 4 weeks preceding the Screening visit through the final visit will be recorded in the CRF.

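### The protocol's adverse event reporting period runs at least 30 days after the last dose, but the last scheduled contact, where recording ends, may fall on Day 28

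*Protocol*

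**What the plan says.** Protocol Section 7.2.2 has AE reporting cover "the period from signature of the informed consent to the end of the study treatment follow-up". It then fixes the length of that follow-up: "the study treatment follow-up is defined as a minimum of 30 days following the last administration of study treatment".

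The contact meant to collect those events is described in three places:

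- **Protocol 5.2.5**, and 3.1 in the same terms, times a follow-up call "At least 4 weeks after a subject's last dose of SBC-103 is administered", unless a follow-up visit is already scheduled. This is a floor counted from the last dose.
- **The telephone footnote in Appendix A** drops the floor: "A telephone follow-up call will be made 4 weeks after the last dose received of SBC-103 after Week 156 End of Treatment". It applies the same timing after early termination.
- **The Week 160 column of Appendix A** carries the call with a ±5-day window. Dosing ends in the Week 156 column, and nothing is scheduled after Week 160.

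Protocol 7.3 sets the end of recording: "AEs will be recorded from the time of signing of the informed consent until completion of the last scheduled visit", which it identifies as the follow-up visit. Events still ongoing are then followed for the period in 7.2.2, but the case report form is no longer updated.

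SAP 7.3.2 summarises AEs up to the final procedure of the final study visit and mentions no 30-day limit. SAP 5.2.1 defines a treatment-emergent event as any AE after first dose, with no end date.

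**The concern.** The protocol gives two different ends to AE collection. One is a duration of at least 30 days. The other is an event, the final contact, which is nominally placed at 28 days. Where they differ, the site's working documents (the schedule and Section 7.3) favour the earlier one.

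Incidence of AEs and serious AEs is part of the primary endpoint, and safety is the main content of the reduced study report that the SAP describes. An event with onset after the final call but before Day 30 falls inside the period in which it must be reported, yet no scheduled contact would bring it to light. With 5 subjects, each subject is 20 percentage points (1/5) of any patient-level incidence. One uncaptured event can therefore change a tabulated figure if that subject has no other event in the same category.

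The SAP adds a smaller ambiguity. Its cut-off is worded in terms of a visit procedure, whereas the planned last contact is a telephone call. Read literally, that leaves open whether events reported in the call are counted.

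**Working it through.** Only date arithmetic is needed. Days are counted from the last dose.

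**Inputs**
- Required follow-up: at least 30 days (Protocol 7.2.2).
- Last dose at Week 156; final call at Week 160, window ±5 days (Appendix A).
- Floor on the call: 4 weeks, or 28 days, after the last dose (Protocol 3.1 and 5.2.5).
- Planned periods: up to 4 weeks of screening, 156 weeks of treatment, 4 weeks of follow-up (Protocol 3.1).

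**The plan's own figure.** 4 + 156 + 4 = 164 weeks, which reproduces the stated total of approximately 164 weeks. That total therefore contains a 28-day follow-up, not a 30-day one.

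**Nominal call.** (160 − 156) × 7 = 28 days. Shortfall: 30 − 28 = 2 days.

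**Call at the early edge of the ±5-day window.** 28 − 5 = Day 23. Shortfall: 30 − 23 = 7 days. Day 23 is inside the column's window but breaks the 28-day floor, so these passages also disagree on the earliest permitted call.

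**Which call days meet the 30-day minimum**

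| Rule applied | Permitted days | Days before Day 30 |
|---|---|---|
| ±5-day window alone | 23 to 33 (11 days) | 23 to 29 (7 of 11) |
| Window plus 28-day floor | 28 to 33 (6 days) | 28 and 29 (2 of 6) |
| Window, floor and 7.2.2 together | 30 to 33 (4 days) | none |

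The last row is not empty, so a site can comply with every passage.

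**Size against planned observation.** Treatment plus 30 days is 156 × 7 + 30 = 1,122 days.
- 2/1,122 = 0.2%
- 7/1,122 = 0.6%

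**Which events are exposed**
- Serious events judged related to treatment stay reportable at any time after the study (7.2.2). Section 7.3 extends this to serious events possibly related to study treatment or to taking part in the study.
- Infusion-associated reactions are defined mainly by onset during the infusion or within 4 hours after it (7.1.3), so a gap from Day 28 hardly touches them.
- What remains is mainly new-onset non-serious AEs and serious AEs judged unrelated.

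**After the change.** With the call at Day 30, the shortfall is 0 and the total is 4 + 156 + 30/7 = 164.3 weeks, still approximately 164.

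**The case against.** The strongest reply is that the passages can all be met at once. A call on Days 30 to 33 satisfies 7.2.2, the 4-week floor and the Week 160 window. Section 7.2.2 also imposes a reporting duty that does not depend on a scheduled contact. This stands: the protocol permits a short follow-up and does not require one. It does not remove the mismatch, because the footnote directs the site to 4 weeks and Section 7.3 ends recording there.

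The second reply is that Day 23 is not compliant, since Sections 3.1 and 5.2.5 rule out a call before 28 days. This also stands. With the floor enforced, the shortfall is at most 2 days. The 7-day figure shows what follows if the conflicting minus side of the window is used.

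A reader might go further and note the Appendix A statement "All study visits will be scheduled relative to Day 0". If the last infusion came 5 days late and the call 5 days early, both counted from Day 0, the interval would be 28 − 5 − 5 = 18 days, 12 short of 30. The documents do not support that reading. Section 5.2.5 and the call's own footnote count from the last dose, so a late infusion moves the call with it.

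Finally, it may be said that the SAP needs no change because its cut-off moves with the last visit. That is only partly right, since the last contact is planned as a call and the SAP refers to a visit procedure.

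**Conclusion.** The mismatch is real and stands in current text: a period of at least 30 days in 7.2.2, against a final contact at 28 days that closes AE recording. The core shortfall is 2 days. It reaches 7 days only if the minus side of the Week 160 window is allowed to override the 4-week floor.

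A reader might infer that AE incidence is biased downward. The documents do not show that. No post-treatment incidence is a planned analysis, the SAP is descriptive with no inferential analysis, and serious events related to treatment remain reportable. The supportable statement is that a few late events, mostly non-serious or unrelated, could go uncaptured in up to 5 subjects.

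The 0.2% and 0.6% figures assume the full 156 weeks of treatment. The SAP records that the development programme was stopped in July 2017. If treatment ended early, the same gap would be a larger share of a shorter observation period, though no longer in days. The documents reviewed do not give actual treatment durations.

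The point is worth correcting because it concerns how primary-endpoint data are collected and costs almost nothing to settle.

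**What to change.** Set one end of AE collection and use it throughout:

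- Place the final call no earlier than the end of the 30-day period in Protocol 7.2.2, counted from the actual last dose, with a plus-only window.
- Bring Protocol 3.1, 5.2.5, 7.2.2 and 7.3, the Week 160 column and its telephone footnote into line with that rule. This also removes the conflict between the ±5-day window and the 4-week floor.
- In SAP 7.3.2, count AEs through that final contact, and name it as a telephone call so that the cut-off is not read as the last visit procedure.

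The cost is a wording change and one call per subject moved by a few days: 2 from the nominal Day 28. No visit, sample or procedure is added. For subjects whose final call has already taken place, only the SAP clarification can still be applied.
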